## *Patient Selection*

***Study 1 (Aim 1): The implementation of a practice-based social determinants of health screening and referral intervention in two pediatric hematology clinics to field test key study logistics and understand the facilitators and barriers to implementation and accelerate its adoption***

The site PI at each institution will help us identify staff members. The BMC-based team will provide an information sheet about Aim 1 of the study in advance so that practitioners and staff have time to consider the consent and come to the focus groups ready with questions regarding the consent. Before beginning the focus groups, the study PIs ([name]) and members of the research team will meet with clinic stakeholders at their staff meetings and provide an overview of the study. All eligible participants will be told that taking part in the research is voluntary and that the decision to not take part will not result in any loss of benefits to which they are entitled to or effect their employment. We

will schedule the focus groups at convenient times for the staff such as prior to beginning of a clinic session or during staff meetings. The Boston Medical Center-based team will conduct focus groups with pediatric hematology clinic staff every six months throughout the study period. We expect that there will be staff turnover during the study and we will be in regular communication with the medical director to monitor and make sure the research team is aware of this.

***Study 2 (Aim 2): Obtaining population-specific empirical estimates of study parameters to plan a future large-scale cluster RCT of WE CARE for children with SCA***

Eligible study participants will be identified by the research staff by reviewing the clinic schedule in advance. We will also ask front desk personnel to assist us in identifying potential subjects, if they are willing, and, in some sites, to assist in handing out informational flyers. If a family is identified as likely to meet eligibility criteria, a member of the study team will approach potentially eligible parents in a private location at the practice, such as an exam room. If the parent is eligible for the study, a study team member will review the study with him/her..

***Study 3 (Aim 3): Qualitatively assess possible mechanisms linking SDoH interventions to improved health outcomes, such as increasing a parent's ability to manage their child's disease through medication adherence***

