***Description of Study Treatments or Exposures/Predictors***

**WE CARE SDoH Screening and Referral intervention:** WE CARE is a relatively simple intervention that has two key components: (1) the WE CARE SDoH Screening Survey and (2) SDoH Community Resource sheets. The intervention will be fully implemented at two of four study sites, after which subjects will be enrolled to collect the outcomes described on pages 7-8, *Definition of Primary and Secondary Outcomes/Endpoints*.

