**Table 1. Summary of the WE CARE Components.**

Key Components:	Description
WE CARE SDoH Screening Survey (see attachments)	Administered at all visits Identifies 6 unmet material needs and parent desire for assistance with: childcare, employment, food security, utilities (heating/cooling, water, electricity), housing, inadequate education 3 rd grade reading level; 0.92 test-retest reliability of original survey 
SDoH Community Resources	One-page information sheets listing available resources 5 th grade reading level

***Component 1: WE CARE SDoH Screening Survey.*** The survey consists of 12 questions designed to: (1) briefly identify 6 unmet material needs (e.g., childcare, employment, food security, household heat,

housing inadequate education) by self-report (e.g., “Are you employed?”) and (2) using a family-centered approach, determine whether parents would like assistance with each problem (i.e. “If no, do you want help?”). Parents wanting help will receive a resource referral (see below). The survey has been translated into Spanish. Because it is a component of the practice-wide implementation of the WE CARE SDoH screening and referral program, the survey will be given at all visits by the front desk staff to all parents of SCA patients who present to the pediatric hematology clinic—not solely to caregivers who enroll in the study. The front desk staff and/or research staff will instruct parents to complete the screener. Clinic staff will be trained to review the WE CARE SDoH survey at visits and to provide community resource information sheets to parents with needs (see below). The completed surveys will be scanned into the EHR.

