Eligible study participants will be identified by the front desk staff and research staff at each clinic. Prior to each clinic session, the research staff will identify potentially eligible study subjects by reviewing the daily appointment list. We will also ask front desk personnel to assist us in identifying potential subjects, if they are willing, and, in some sites, to assist in handing out informational flyers. If a family is identified as likely to meet eligibility criteria, a member of the study team will approach potentially eligible parents in a private location at the practice, such as an exam room. If the parent is eligible for the study, a study team member will review the study with him/her. Informed consent will be obtained via written consent. The original hard copies of the ICFs will be stored in a locked file in a locked room in the hematology research space at that site. Each clinical site will maintain a tracker linking each patient to a unique subject ID number, which does not contain any combination of information that allows the identification of a subject; this tracker will not be shared outside that clinical site. Participants will be provided with a copy of their signed informed consent form.

Data will be collected from parents primarily from parent-administered surveys at enrollment and at follow-up which will occur one year post-index visit. These surveys will be completed using a study tablet (e.g., iPad) and backed up on to a HIPAA-compliant Boston Medical Center installation of REDCap, which is backed up on the secure, password-protected Boston University Medical Campus server. To complete these surveys, subjects will enter their unique ID number. A brief telephone interview will be conducted 3, 6, and 9 months post-enrollment to ascertain unmet needs, contact and enrollment in community-based resources, and parent report of prescription refills for penicillin or hydroxyurea. A hair cortisol sample will also be collected from the parent at enrollment and 1-year follow-up. Finally, site research staff will collect data from the electronic health record (EHR) on child health outcomes (i.e., adherence to clinic visits, medication adherence, ED visits, hospitalizations, vaso-occlusive episodes, acute chest syndrome, and infections). Data from the EHR will be collected three times (baseline, 6-months post-enrollment, and 12-months post-enrollment).

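### Aim 2 families are recruited after site allocation is known, with front desk and flyer use that varies by site and no rule to approach every eligible family, so the arms could enrol different families

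*Combined protocol and SAP*

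**What the plan says.** All references are to the combined protocol and SAP.

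- **Allocation and timing.** Study Design (Study 2) randomises four sites, two per group. Description of Study Treatments or Exposures/Predictors adds: "The intervention will be fully implemented at two of four study sites, after which subjects will be enrolled to collect the outcomes".
- **Who finds families.** Patient Selection (Study 2) says: "Eligible study participants will be identified by the research staff by reviewing the clinic schedule in advance". Data Collection Methods (Study 2) says: "Eligible study participants will be identified by the front desk staff and research staff at each clinic". It then gives the working step: "the research staff will identify potentially eligible study subjects by reviewing the daily appointment list".
- **Extra routes.** Both sections also ask front desk personnel to help find families, "if they are willing, and, in some sites, to assist in handing out informational flyers".
- **Who makes contact.** "a member of the study team will approach potentially eligible parents in a private location at the practice".
- **Who delivers the intervention.** Under Component 1, below Table 1, "the survey will be given at all visits by the front desk staff to all parents of SCA patients". Front desk staff, research staff or both tell parents to fill it in.
- **Reporting.** The Aim 2 part of the Data Analysis Plan counts parents from contact through to enrolment, with reasons for refusal. The only breakdown it names for these counts is gender.
- **Adjustment.** The mixed models adjust for sociodemographics, types of social need, cumulative needs and services received.
- **Use of results.** Statistical Power and Sample Considerations says the pilot will not be used to judge efficacy. It also says that control-group estimates will feed the power calculation of the next trial.

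**The concern.** Randomising sites makes the sites comparable in expectation. It does not do so for the families enrolled later by people who know the allocation. If families at intervention sites come in by a different route from those at control sites, the arms can differ in need, motivation or underlying emergency department (ED) use before WE CARE has any effect.

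Aim 2 exists to produce planning estimates: recruitment and refusal rates, between-arm differences with effect sizes, and control-group values. All of them depend on who is enrolled. Enrolment in community resources, one of the listed primary outcomes, is especially exposed because it depends on a family's needs and readiness to act. If routes differ between sites and this is not logged, the next trial's planners cannot separate a site's recruitment method from its patient population.

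**Working it through.** The plan states no figure on this point, so the check is mainly a comparison of its sections.

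**1. Is allocation known at recruitment?** Yes. Enrolment follows full implementation at the intervention sites. As far as the extracted Study Timeline can be read, Aim 2 accrual starts one quarter after the implementation row starts and runs for five quarters. No section lists families before allocation or provides a recruiter unaware of allocation.

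**2. Do those who find families overlap with those who deliver WE CARE?** Partly, and only at intervention sites. Front desk staff hand out the survey there and may also point out families. Research staff do the main screening, but Component 1 allows them to instruct parents on the survey, so they too may take part in delivery.

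**3. Is the method the same everywhere?** The core is: research staff review the list and a study team member approaches. The additions are not, since front desk help depends on willingness and flyers on the site.

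**4. How easily does a site difference become an arm difference?** The target is 35 families at each of 4 sites: 35 × 4 = 140 families, 70 per arm. Each site is 35/70 = half of its arm, so a shift of x points in one site's recruited mix moves the arm by x/2.

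The number of flyer sites is not given. Suppose flyer use is unrelated to allocation. There are C(4,2) = 6 ways to assign sites two and two.

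| Sites using flyers | Chance that the arms have unequal numbers of flyer sites |
|---|---|
| 1 or 3 | 6/6 (equal split impossible) |
| 2 | 2/6 (both in the same arm) |

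Imbalance between arms is therefore likely or possible, but not certain.

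**5. Is there a rule on whom to approach?** None is stated: neither consecutive approach, nor approach to all listed families, nor an order.

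**6. Would a difference be seen?** Counts start at contact, so eligible families who were never approached do not appear. No table by site or arm is specified. ED visits are collected at baseline (Definition of Primary and Secondary Outcomes/Endpoints), so imbalance on that measure could be checked. Baseline ED use is not named among the model covariates.

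**7. Would adjustment remove it?** Only for measured characteristics. Because enrolment at intervention sites follows implementation, needs and services recorded at enrolment may already reflect WE CARE, and so may not be clean baseline variables.

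**8. Can the bias be sized?** Let f be the share of an arm's families who enter by a selective route, and d the difference between their underlying ED-visit proportion and that of the eligible population. The bias in the comparison is f₁d₁ − f₀d₀ (intervention minus control). The documents give no f, no d and no count of eligible families. Purely as an assumption, take f = 20–50% and d = 10–20 points in one arm and no selection in the other. The result is 0.2 × 10 = 2 to 0.5 × 20 = 10 points, against the 25-point difference in the power section (10/25 = 40%). The sign of d is unknown, and equal selection in both arms would cancel.

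**The case against.** The case on the other side is substantial.

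- **The front desk role is supplementary.** Research staff screen the list at every site and a study team member makes every approach. A prompt can add a name but cannot remove one from the list. This stands. A reader might infer that front desk staff choose the sample; the documents do not support that. What remains is that nothing obliges staff to approach everyone on the list, so prompts can still influence who is reached.
- **The two descriptions do not conflict.** A reader might see a contradiction between research staff alone in Patient Selection and both groups in Data Collection Methods. Patient Selection goes on to give the same front desk and flyer provisions, so there is none of substance.
- **The front desk is not said to see needs.** It hands the survey to all parents of children with sickle cell anemia. Clinic staff are trained to review it and providers give out the information sheets. Whether the front desk reads the answers is not stated.
- **Variation by site is not variation by arm.** This stands as logic: flyers could be used at one site in each arm. With four sites, an uneven split is still easy to get.
- **There may be little room to select.** Eligibility is narrow, and 35 is a target. If sites must approach almost everyone to reach it, selection is small. No eligible counts are given, so this cannot be settled either way.
- **It is a pilot.** Efficacy is disclaimed, and the dual role of the front desk cannot affect control sites. But optional help, site-specific flyers and the absence of an approach rule apply at control sites too, and those sites supply the planning values. Between-arm effects are also still estimated.

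**Conclusion.** The concern holds as a possibility that the plan leaves open, not as a demonstrated bias. Recruitment follows known allocation, the supplementary routes differ by site, and no rule requires every eligible listed family to be approached. With two sites per arm, the enrolled families could differ between arms for reasons unrelated to WE CARE. The planned adjustment covers only measured differences.

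Size and direction are unknown. A reader might infer a bias of 2–10 points, or up to 40% of the planned 25-point difference. That range rests wholly on assumed inputs and on selection in one arm only, so it should not be cited as an estimate.

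This is a cheap improvement. It does not invalidate a pilot that disclaims efficacy, but it does bear on the recruitment rates, between-arm estimates and control-group values that the pilot is meant to deliver.

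**What to change.** **Patient Selection and Data Collection Methods (Study 2).** State one method for all four sites: research staff approach every eligible family on the appointment list, consecutively as they attend, until the 35-family target is met. State also that front desk prompts and flyers do not decide who is approached. If they are kept, use them identically at all four sites. Give the same description in both sections.

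**Data Analysis Plan (Aim 2).** Add a table of eligible, approached, refusing and enrolled families by site and arm, with basic characteristics such as child age, prescribed drug and language.

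**Cost.** A screening log at each site and possibly slightly slower recruitment. Research staff already review the appointment list before each clinic session, so the plan needs no new screening step. If recruitment has already begun, the log and the table by site and arm can still be introduced for the remaining families.

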### ***Definition of Primary and Secondary Outcomes/Endpoints***

Because qualitative research is by nature exploratory, we have not defined outcomes for the focus group discussions with practice staff (**Aim 1**); however, we will use the Promoting Action on Research Implementation in Health Services (PARIHS) framework to guide these discussions about facilitators and barriers to WE CARE implementation. Key areas of exploration will be (1) evidence: attitudes and beliefs about evidence of the WE CARE system; (2) context: organizational, systemic, and sociopolitical features that promote or hinder implementation of WE CARE; and (3) facilitation: attributes of the facilitation that supported or impeded the implementation, and needed adaptations.

Primary outcomes for **Aim 2** include the following:

- *Identification of unmet needs and provision of referrals.* Previously utilized forms will be used during baseline and follow-up questionnaires to measure whether practitioners provided families resource handouts.
- *Parental enrollment in community-based resources.* Baseline and follow-up questionnaires to measure enrollment in community resources.
- *Process measures.* Data will be collected on adherence to clinic visits (appointments kept, cancelled, and no-show). We will collect data on medications adherence in two ways. First, we will collect laboratory markers that are commonly affected by HU, including hemoglobin and hemoglobin F levels, white blood cell and absolute neutrophil counts, and MCV. We will also collect data on prescriptions written and filled for HU and penicillin through EHR review and parent report.
- *Health outcomes:* Data on vaso-occlusive episodes, acute chest syndrome and sepsis will be collected from the EHR at 6-month- and 12-month follow-up. Quality of life will also be assessed through both the PedsQL, which has been validated in children with sickle cell disease and is responsive to change, and the PedsQL Sickle Cell Disease Module.
- *Healthcare utilization outcomes:* Data on emergency department visits, hospitalizations, and clinic visits will be collected from the EHR at baseline and 12-month follow-up. We have chosen

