*\*Research Electronic Data Capture (REDCap) is a research focused, electronic web-based data capture system. REDCap is a data collection tool and allows for storage and management of both surveys and databases. REDCap is a secure storage system and meets HIPAA compliance standards. REDCap software will be used to facilitate parent consents, questionnaires, and forms.*

**Materials.** The research data will include questionnaires completed by parents/caregivers both in-person and via telephone, parent hair cortisol samples, and medical chart review. Only trained project staff at each clinical site will have access to participants' identifying information.

For the hair cortisol samples, we will be following the hair collection protocol developed by [name] from the University of Massachusetts (UMASS). Hair will be cut at the level of the scalp from 2-3 locations and cut to 3cm at the distal end. Hair samples will be placed directly into a plastic vial; each vial will be labeled by an ID number uniquely linked to each study subject (see below). Hair cortisol is stable at room temperature indefinitely, thus vials will be stored in a locked file cabinet.

For the *medical chart review*, existing trained research staff members at each study site, will collect the data. We decided to use existing research staff for the data collection component of the study since getting chart review credentialing is difficult at each of the study sites. At baseline and 12-month follow-up, medical charts will be reviewed in order to determine the number of appointments kept versus cancelled or no-show, the number of days covered by prescription refills for penicillin and hydroxyurea, and blood tests for monitoring hydroxyurea (including WBC, HB F%, and MCV). At 6-month and 12-month follow-up, medical charts will be reviewed in order to determine the frequency of vaso-occlusive episodes, acute chest syndrome, and sepsis diagnoses.

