***Aim 2. Obtain population-specific empirical estimates of study parameters to plan a pragmatic large-scale cluster RCT.*** We will summarize the number of parents contacted, lost to follow-up, refusing participation, and enrolled. We will examine this by gender (e.g., father vs. mother). We will note reasons for refusals. We will determine parents' recruitment and attrition rates and receipt of WE CARE using descriptive statistics. We will also determine the data collection completion rate, including hair cortisol, for each data time point (baseline, 3-, 6-, 9-, and 12-month follow-up) via descriptive statistics. Each outcome and process variable described above will be first transformed into its final composite value/score. We will calculate within-group mean and standard deviation of our SDoH, process, mediator and health utilization and health outcome variables. We will also break down the intervention group into two subgroups differentiated by whether parents enrolled in resources at follow-up, and explore any differences. An intention-to-treat approach will be used to explore differences between the intervention and control groups. We will also report all data disaggregated by gender. Two independent sample t-test and chi-square tests will be used to determine bivariate differences. Mixed effects regression models will be used to estimate the effect size of the intervention on SCA outcomes accounting for baseline differences in sociodemographics, types of SDoH, cumulative needs, receipt of services, and *a priori* determined covariates (i.e. sociodemographic characteristics). To explore potential moderators for the intervention effect at the parent, child and family levels (e.g., gender, race, ethnicity, age, language, household income), we will use Rothman's methodology; specifically, we will conduct stratified analyses for each potential moderator followed by using standard interaction terms in our models. We will also explore mediation of our hypothesized potential mediators between SDoH and the intervention with each SCA health outcome using the approach recommended by MacKinnon, Lockwood, and Williams. We will account for the clustering by study site by calculating the intraclass correlation.

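### The EHR collection schedule differs between sections, so disease complications may have no baseline count; one event is named two ways, and the model does not list the outcome's own baseline

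*Combined protocol and SAP*

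**What the plan says.** Four places in the protocol schedule the EHR data for Aim 2.

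- **Definition of Primary and Secondary Outcomes/Endpoints.** Complications: "Data on vaso-occlusive episodes, acute chest syndrome and sepsis will be collected from the EHR at 6-month- and 12-month follow-up". Utilization: "Data on emergency department visits, hospitalizations, and clinic visits will be collected from the EHR at baseline and 12-month follow-up". The same section names ED visits as the primary outcome.
- **Data Collection Methods, Study 2, medical chart review paragraph.** Complications: "At 6-month and 12-month follow-up, medical charts will be reviewed in order to determine the frequency of vaso-occlusive episodes"; the full set is "vaso-occlusive episodes, acute chest syndrome, and sepsis diagnoses". Other items: "At baseline and 12-month follow-up, medical charts will be reviewed in order to determine the number of appointments kept versus cancelled or no-show", together with days covered by refills and blood tests. ED visits and hospitalizations do not appear in this paragraph.
- **Data Collection Methods, Study 2, Study Procedures.** The child outcomes taken from the EHR include "ED visits, hospitalizations, vaso-occlusive episodes, acute chest syndrome, and infections", and the next sentence reads "Data from the EHR will be collected three times (baseline, 6-months post-enrollment, and 12-months post-enrollment".
- **Data Management Methods, Aim 2.** It gives nearly the same list, again with infections, and the same three time points. Medication adherence is in the Study Procedures list but not in this one.

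The Data Analysis Plan for Aim 2 describes mixed effects models "accounting for baseline differences in sociodemographics, types of SDoH, cumulative needs, receipt of services" and prespecified sociodemographic covariates. The baseline value of the outcome being modelled is not in that list.

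**The concern.** Research staff at each of the four hospitals do the abstraction separately, and the hospital is the unit of randomization, two per arm. A site that follows the chart-review paragraph will have no pre-enrollment count of vaso-occlusive episodes, acute chest syndrome or sepsis; a site that follows the Study Procedures will have one. A site that counts infections will record a broader event than a site that counts sepsis, and with two sites per arm that difference cannot be told apart from an arm difference. The Quality Control Method has each research assistant re-review visits at his or her own site and describes no cross-site check, so it would not reliably expose a difference in interpretation between hospitals.

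The gap also bears on the purpose of Aim 2, which is to estimate parameters for a larger trial. The correlation between a child's baseline and follow-up event counts is one such parameter, and it cannot be estimated for the complications without a baseline count. Prior disease severity is also likely to predict later events, so leaving it out of the model gives up precision and leaves measured severity differences between arms unadjusted.

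**Working it through.** **Step 1. Set the schedules side by side** (months; 0 = baseline).

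| Variable | Outcome section | Chart-review paragraph | Study Procedures and Data Management |
|---|---|---|---|
| Vaso-occlusive episodes, acute chest syndrome | 6, 12 | 6, 12 | 0, 6, 12 |
| Sepsis / infections | sepsis: 6, 12 | sepsis: 6, 12 | infections: 0, 6, 12 |
| ED visits, hospitalizations | 0, 12 | not listed | 0, 6, 12 |
| Clinic visits / appointments | 0, 12 | 0, 12 | 0, 6, 12 |

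Each row shows a mismatch. No section defines a look-back window for any of these reviews.

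**Step 2. Size the gain from a baseline covariate.** The documents give no figure for this, so there is none to reproduce. Inputs:

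- m = 35 families per site and an ICC ρ no larger than 0.01, both from Statistical Power and Sample Considerations.
- r, the baseline to follow-up correlation within site: assumed, 0.5 to 0.7.
- ρ = 0.05: assumed, as a less favourable case.
- The covariate is taken to explain within-site variance only.

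The variance of a site mean is proportional to (1 − ρ)/m + ρ. Adjustment multiplies the within-site part by 1 − r². Multiplying through by m, the variance factor is

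[(1 − ρ)(1 − r²) + mρ] / [(1 − ρ) + mρ].

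| ρ | r | Variance factor | SE multiplier | SE reduction |
|---|---|---|---|---|
| 0.01 | 0.5 | (0.99 × 0.75 + 0.35)/1.34 = 0.815 | 0.903 | about 10% |
| 0.01 | 0.7 | (0.99 × 0.51 + 0.35)/1.34 = 0.638 | 0.799 | about 20% |
| 0.05 | 0.5 | (0.95 × 0.75 + 1.75)/2.70 = 0.912 | 0.955 | about 4% |
| 0.05 | 0.7 | (0.95 × 0.51 + 1.75)/2.70 = 0.828 | 0.910 | about 9% |

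The formula is for a continuous outcome. For event counts it is a guide to size only.

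**Step 3. Check whether a 12-month look-back from enrollment would be a true baseline.** The intervention description says WE CARE is in full use at the two intervention sites before families enroll, and that the survey goes to all parents of SCA patients whether or not they enroll. In the Study Timeline, as the table was extracted, assessment of the implementation starts in Year 1 quarter 3. Accrual runs from Year 1 quarter 4 to Year 2 quarter 4, which is five quarters. If WE CARE starts with the assessment row, a family enrolled in Year 2 quarter 4 enrolls at least four quarters after the quarter in which WE CARE began. Most or all of its prior 12 months would then fall under the intervention. Eligibility starts at age 0, so children under one year have no full 12 months in any case.

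**The case against.** The strongest reply is that the sections are detail and summary of one scheme. The outcome section and the chart-review paragraph agree with each other on the complications, on appointments and on sepsis, and their occasions {0, 12} and {6, 12} together make up the three collection times given elsewhere. That reading is possible. It does not settle the matter: the Study Procedures and Data Management sections attach the three times to the whole list without a split, the reading still leaves the complications without a baseline, and it does not explain the two event names.

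It is also fair to say that this is a pilot that disclaims efficacy conclusions and will take its planning estimates from the control group, so precision of the treatment effect is not its main product. That limits the weight of the point but does not remove it, since comparable event counts across sites and baseline correlations are themselves planning inputs.

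Several stronger inferences are tempting, and the documents do not support them:

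- *That the primary outcome lacks a baseline.* The outcome section collects ED visits and hospitalizations at baseline.
- *That data are lost without a 6-month ED review.* EHR events can be abstracted retrospectively, and a 12-month review can cover the whole year.
- *That the precision gain is 13 to 29%.* That follows from 1 − r² alone (SE multipliers 0.87 and 0.71) and ignores clustering by site.
- *That a fixed prior-12-month count could be added at no risk.* Step 3 shows it can overlap exposure to WE CARE at intervention sites; adjusting for it could then remove part of the effect.
- *That sites are in fact counting different events.* The text permits this; nothing shows that it happens.

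**Conclusion.** The inconsistency stands on the text and needs no assumption. Two sections give vaso-occlusive episodes, acute chest syndrome and sepsis no baseline review; two others do, and name infections instead. ED visits are missing from the chart-review paragraph, and the mixed model does not list the outcome's own baseline even where that value is collected.

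The statistical cost is moderate and conditional. With r between 0.5 and 0.7, standard errors would fall by about 10 to 20% at ρ = 0.01, or about 4 to 9% at ρ = 0.05, if the covariate explains only within-site variance. A covariate that also explained differences between sites would gain more, but the documents do not show that it would. No sample-size or power figure in the plan changes. Baseline adjustment reduces measured severity imbalance; a reader should not infer that it separates hospital from intervention, which a child-level covariate cannot do with two sites per arm. The change should be made, but it is not a condition for the pilot to proceed.

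**What to change.** 1. Replace the scheduling text in the four places with one table of EHR variables by time point, and state the look-back window for each review.
2. Add ED visits and hospitalizations to the chart-review paragraph. A separate 6-month ED review is not needed if the 12-month review covers the full year.
3. Use one defined event term at all four sites. Sepsis, as in the outcome section, is the natural choice.
4. At the existing baseline chart review, count ED visits, hospitalizations, vaso-occlusive episodes, acute chest syndrome and sepsis over a window that ends before WE CARE began at the intervention sites, with the same calendar window at control sites. Record observed person-time, so that infants contribute a rate.
5. Enter each outcome's pre-implementation count or rate as a covariate in its mixed model, and say how children without such history are handled.

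The cost is protocol wording and a few extra abstraction fields in a review already done at baseline. The remaining limitation is that the youngest children, in particular those born after WE CARE began, will have no usable pre-implementation history.
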